6.3.2 API Preclinical Composite Cognitive (APCC) battery

The APCC score will be derived from the following seven tests performed as part of the cognitive scales administered during the study (see [Table 6-1](#) Assessment schedule)

- MMSE:
 - Orientation to Time
 - Orientation to Place
- RBANS:
 - List Recall
 - Story Recall
 - Coding
 - Line Orientation

- Raven's Progressive Matrices – subset

All scales used to derive the APCC test score (RBANS, MMSE and Raven's) will be administered twice during screening: first to assess inclusion (V101 and/or V103) and a second time prior to randomization (baseline pre-dose). A minimum interval of 4 weeks should be respected between two administrations of the APCC scales or CDR.

Of note: In case a repeat assessment of CDR and RBANS is required during screening to confirm unimpaired cognition (see [Section 6.1.6.1](#)), CDR and RBANS can be repeated 5 days before the scheduled Randomization (using the Baseline scales that include RBANS Form A, and the other APCC scales).

Refer to [Appendix 2](#) for details on assessment from study partner and conditions of administration/presence at visits.

6.3.3 Mini Mental State Examination (MMSE)

The MMSE is a brief, practical clinician reported outcome that examines cognitive status ([Folstein et al., 1975](#)). It evaluates orientation, memory, attention, concentration, naming, repetition, comprehension, and the ability to create a sentence and copy two intersecting pentagons.

The test consists of five sections (orientation, registration, attention, recall, and language) with a total score ranging from zero to 30. A higher score indicates better cognitive function. The 5 sub scores as well as the total score will be recorded.

Although all components of the MMSE will be assessed, for calculation of the APCC test score, only the Orientation to Time and Orientation to Place scores from the MMSE (each of which ranges from zero to five) will be used. MMSE will be performed at Screening part I first (by regular site personnel, no certification required) and then at baseline pre-dose and every 6 months by a certified rater. If MMSE is not available from previous 3 months source data, it should be collected a V101. If it is administered by a non-certified rater (allowed at V101 only) record on a paper form, do not upload to Virgil. If administered by a certified rater at V101 on Virgil, then no need to repeat at V103.

During the study, the test will be administered and collected using the Virgil[®] tablet, except for the MMSE drawing and sentence pages that will be paper based. Pictures of the drawing and sentence will be taken and uploaded electronically to the tablet.

6.3.4 Repeatable Battery for the Assessment of Neuropsychological Status (RBANS)

The RBANS ([Randolph, 1998](#)) is a clinical tool that was specifically designed for both diagnostic purposes and for tracking change in neurocognitive status over time. One of the key design goals of the battery is to detect and characterize the earliest neurocognitive changes associated with the earliest stages of dementia. The RBANS has no floor or ceiling effects in either cognitively normal older adults or in patients with amnesic MCI, despite the fact that these two groups have mean scores on the RBANS nearly two standard deviations apart ([Karantzoulis et al 2013](#)). RBANS scores have been reported to be correlated with cerebral amyloid in both cognitive normal individuals ([Duff et al 2013](#)) and in patients with MCI due to

AD ([Mukai et al 2015](#)).

The RBANS is relatively brief (< 25 minutes) to administer, has four equivalent alternate forms, and 25 linguistically- and culturally-validated translations. The RBANS generates age-adjusted index scores for five neurocognitive domains which are used to calculate a Total Scale Index score.

The RBANS is comprised of the following domains, with associated subtests used for Index scores:

- Immediate Memory – List Learning and Story Memory (IMI)
- Visuospatial/Constructional – Figure Copy and Line Orientation
- Language – Picture Naming and Semantic Fluency
- Attention – Digit Span and Coding
- Delayed Memory – List Recognition and Sum of (List Recall, Story Recall, and Figure Recall; DMI)

The RBANS Delayed Memory index score is used as an inclusion criterion, together with the CDR global score, to ensure selection of participants with unimpaired cognition at screening. With a normal mean score of 100 and standard deviation (SD) of 15, the 85 and 70 cut-offs for inclusion correspond to 1SD and 2SD below the normal mean, respectively. Participants who score between 85 and 70 will be considered suitable for the study only if their CDR global score is zero, confirming the absence of any clinically-detectable memory decline.

RBANS comes in four different versions labeled A, B, C, D. Form B will be used at screening (and repeat screening, if needed), while Form A will be used at baseline, Form D at month 3 and Form C at month 6. Subsequent visits during the Treatment Phase will follow the pattern: Form D, B, A, C / D, B, A, C and so on.

6.3.5 Raven's Progressive Matrices

Raven's Progressive Matrices ([Raven et al 2000](#)) is a non-verbal, multiple choice measure of general ability and reasoning using a visual modality. It was designed to be culturally nonbiased, as neither language nor academic skills are required to answer items successfully. The test requires conceptualization of spatial design and numerical relationships with varying levels of difficulty. For each item a participant is asked to identify the missing component to complete a pattern.

Although all components of the Raven's Progressive Matrices Set A and Set B will be assessed, in order to calculate the APCC test score, only a subset of items from Sets A and B will be used (items A2, A4, A8, B1-B6), with a total score from zero to nine.

The Raven's will be administered using a paper-based stimulus booklet, results being captured on the Virgil[®] tablet.

6.3.6 Clinical Dementia Rating Scale - Sum of Boxes (CDR-SOB)

The CDR is a global measure that evaluates cognition and functional performance and is widely used in clinical research in AD ([Morris, 1993](#)). The scale assesses six domains: Memory, Orientation, Judgment & Problem Solving, Community Affairs, Home & Hobbies, and Personal

Care. Each domain is assigned a score, which are summed to obtain the sum of boxes (SOB) score.

The necessary information for assessment is obtained through a semi-structured interview of the participant and a reliable informant or collateral source (i.e. study partner). Descriptive anchors are provided for each score that guide the clinician in making appropriate ratings based on interview data and clinical judgment, in order to evaluate the staging severity of the dementia.

The global CDR scores and CDR-SOB scores will be collected. Global scores range from zero to three, with greater scores indicating greater disease severity. CDR-SOB scores range from zero to 18 with greater scores indicating greater disease severity.

Clinician judgment of MCI due to AD or dementia due to AD and/or a change in the global CDR score (until the established diagnosis of dementia) will trigger the adjudication process (see [Section 8.5](#)).

6.3.8 Everyday Cognition Scale (ECog)

[figure not shown]
The ECog scale measures cognitively-relevant everyday abilities and is comprised of 39 items covering six cognitively-relevant domains: Everyday Memory, Everyday Language, Everyday Visuospatial Abilities, Everyday Planning, Everyday Organization, and Everyday Divided Attention ([Farias et al 2008](#)).

The questionnaire is a self-reported measure completed by both the participant (ECog-subject) and his/her study partner (ECog-informant). All questionnaires will be completed in the language most familiar to the respondent, at the scheduled study visit. The participant should be given sufficient instruction, space, time and privacy to complete the questionnaire on the tablet. The study coordinator (SC) should check the responses to the questionnaire for completeness and encourage the participant to complete any missing responses

Within each domain, ability to perform a specific task is rated on a five-point scale ranging from: 1) no difficulty, 2) mild difficulty, 3) moderate difficulty, 4) severe difficulty, or 5) unable to do.

The total score for the 39 items ranges from 39 to 195, with greater scores indicating worse daily function. The study will include a modified version of the ECog scale to measure a static state (not a change), assessed at regular, six month intervals to minimize recall bias.

Details on the study partner characteristics (relationship and frequency of interaction) are also captured on the ECog-informant.

6.3.13 Appropriateness of efficacy assessments

Postponing the diagnosis of MCI and/or dementia represents an important clinical outcome with high face validity. The core clinical diagnostic criteria proposed by the National Institute on Aging - Alzheimer's Association working group will be used (Albert et al 2011; McKhann et al 2011) and will be assessed and operationalized as described in Section 6.3.1, including a required confirmation at the consecutive 6-monthly visit and a formal adjudication process by an independent Progression Adjudication Committee (see Section 8.5).

Preclinical cognitive decline due to AD is expected to be detectable with the proposed APCC test score. Decline on the APCC test score will provide a continuous measure of cognitive decline associated with progression to the clinical stages of MCI due to AD and/or dementia due to AD. The APCC battery includes well-established, validated cognitive assessments that are expected to be sensitive to detect decline prior to the onset of MCI due to AD or dementia due to AD and continue to measure decline during the clinical course of the disease. The scales will undergo a central review to minimize variability across sites or raters throughout the study. The composite is constructed from validated cognitive assessments across multiple cognitive domains (e.g., episodic memory, executive function, visual-spatial function) that reflect the spectrum of cognitive deficits of AD. Decline in these cognitive domains is associated with and predictive of functional decline in AD (Farias et al 2003). In addition, many of the cognitive domains included in the composite measure have been shown to correspond directly to participant and caregiver concerns in early disease (Ropacki et al 2014). The derivation of the proposed APCC battery and its resulting test score is described in Section 6.4.2.

Secondary endpoints are chosen to evaluate the effects of the investigational drug on other clinical aspects of the disease with a focus on the endpoints likely to assess changes in individuals with preclinical AD and those who expected to progress to MCI.

CDR and its subscore CDR-SOB measure the global clinical function accounting for the input from the study partner which is widely used in clinical research in AD, RBANS total score is a clinical tool used to assess the neuropsychological status. The ECog combines subjective report of both cognitive and instrumental difficulties of daily living obtained from participants, as well as from a study partner who knows the participant well.

Timing of the cognitive assessments at Screening and/or Baseline, 3, 6 and 12 months and then every 6 months will allow monitoring of cognitive, behavioral and functional status.

6.4 Safety

Clinically relevant findings that are present prior to signing Informed Consent must be included in the Medical History part of the CRF. Significant findings made after signature of the ICF which meet the definition of an AE must be recorded on the Adverse Event eCRF page for all participants randomized or treated.

Clinically notable test findings are defined in Appendix 1. Only clinically significant abnormalities should be reported on the eCRF AE page for any of the assessments listed below.

6.4.1 Physical (including skin) and neurological examination

Physical and neurological examinations will be performed by a qualified clinician at visits specified in [Table 6-1](#). Any findings are to be recorded as unscheduled assessment/AE, as per Investigator judgement.

Physical examination will include an examination of general appearance, skin (and skin reactions), neck (including thyroid), eyes, ears, nose, throat, lungs, heart, abdomen, back, lymph nodes, extremities and vascular.

Neurological examinations will include mental status, cranial nerve function, motor function (tone, strength and reflexes), sensory function (small fiber, large fiber and cortical), coordination (cerebellar function) and balance/gait.

Information about both, the physical (including skin) and the neurological examinations must be present in the source documentation at the study site (see [Section 6.4.6](#) for further information on dermatologic findings).

6.4.2 Vital signs

Vital signs include blood pressure, pulse, and temperature (using site equipment) measurements. Systolic and diastolic blood pressure and radial pulse rate will be assessed after the participant has rested in the sitting position for at least three minutes. The vital signs data will be recorded on the corresponding eCRF pages, unless marked for source documentation only in [Table 6-1](#).

6.4.3 Height and weight

Height in centimeters (cm) and body weight (to the nearest 0.1 kilogram [kg] in indoor clothing, but without shoes) will be measured at screening. In addition, weight will be measured at all visits where vital signs are measured.

6.4.4 Laboratory evaluations

A central laboratory will be used for analysis of all specimens collected. Details on the collections, shipment of samples, and reporting of results by the central laboratory are provided to investigators in the Laboratory Manual.

Please refer to [Section 6.1.3](#) for additional laboratory tests required at Screening.

6.4.4.1 Hematology

A standard hematology panel with differential counts will be performed. Hemoglobin (Hb), hematocrit, red blood cell count, platelet count, and white blood cell count with differential count will be measured.

In addition if clinically warranted for participants treated with anti-coagulants, prothrombin time international normalized ratio (PT/INR) may be measured for assessment of coagulation at screening and repeated, if required.

6.4.4.2 Clinical chemistry

A standard blood chemistry panel will be performed: Albumin, total protein, alkaline phosphatase, total bilirubin, calcium, chloride, sodium, potassium, magnesium, inorganic phosphorus, bicarbonate, creatinine, creatine phosphokinase (CPK), C-reactive protein (CRP), Vitamin B12, folate, gamma-glutamyl transferase (γ -GT), lactate dehydrogenase (LDH), cholesterol (total / LDL / HDL), triglycerides, lipase, α -amylase, alanine aminotransferase (ALT), aspartate aminotransferase (AST), glycated hemoglobin (HbA1c), blood urea nitrogen (BUN), uric acid, and thyroid stimulating hormone (TSH) will be measured.

The creatinine clearance will be estimated from serum creatinine concentrations using the Cockcroft-Gault formula. The results should be available and reviewed before the MRI scans if gadolinium injection is required because of findings on previous MRI scans.

6.4.4.3 Urinalysis

Dipstick measurements for specific gravity, protein, glucose, and blood will be performed at the site. In case of clinically significant abnormality, a urine sample will be sent to the central laboratory for analysis of the same parameters and in addition, creatinine, total albumin, albumin/creatinine ratio, white blood cells (WBC) and red blood cells (RBC) sediments.

6.4.4.4 CSF cell count

For participants in whom a CNS-related safety concern arises, an aliquot of CSF will be used for local measurement of CSF cell counts. Cell counts will include erythrocytes (as an indicator of blood contamination) and total white blood cells. The location of the facility where the lumbar puncture procedure is done must take into account that samples can only be analyzed if processed within two hours at the local laboratory facility. The data will be entered on the corresponding eCRF pages.

6.4.5 Electrocardiogram (ECG)

ECGs will be centrally evaluated. Full details of all procedures relating to the ECG collection and reporting will be contained in the technical manual, which is provided to the site by the centralized ECG vendor.

[figure not shown]
Twelve-lead standard ECGs will be recorded in triplicate (one minute apart) after participants have been resting in the supine position for at least 10 minutes. The ECGs should be scheduled approximately 2.5 hours post CNP520 drug administration on site ([Section 5.5.4](#)). If the LDR is 50 mg once weekly and the dosing day corresponds to the visit day then the scheduled is maintained otherwise, the ECG should be taken preferably at the same time of the day than earlier visits.

[figure not shown]
The Fridericia QT correction formula (QTcF) should be used for clinical decisions.

Electrocardiograms will be obtained as designated in the [Table 6-1](#), if applicable.

The ECG readings will be sent automatically to the centralized ECG vendor. Findings at screening, considered as clinically significant and meeting alert values, in the opinion of the investigator, must be discussed with the Novartis Medical Monitor before administration of investigational treatment.

Each ECG tracing must be labeled with study number, participant initials, participant number, date and time, and filed in the study site source documents. For any ECGs with participant safety concerns, two additional ECGs must be performed to confirm the safety finding and copies forwarded to the central ECG laboratory for assessment.

6.4.7 Safety brain MRI scans

Safety MRI will include the following sequences:

- 3D T1-weighted, structural T1 MPRAGE/IR-FSPGR/TFE (with acceleration) (also used for volumetric MRI, see [Section 6.5.3.1](#). Note that this sequence will be captured twice at each scan, and may need a repeat in case of motion)
- Axial FLAIR (for general ascertainment of brain abnormalities including Amyloid Related Imaging Abnormality-Edema (ARIA-E) and for white matter lesions)
- Axial T2 Star/Gradient echo (GRE) (to assess Amyloid Related Imaging Abnormality-Hemorrhages (ARIA-H), including superficial siderosis, and other hemorrhages)
- Axial PD/T2: surrogate to FLAIR with better sensitivity in infratentorial regions
- Axial Diffusion-Weighted Imaging (for assessment of recent infarcts and white matter integrity examination). Diffusion Tensor Imaging (DTI) may be performed at specific sites.
- Only in case of certain new findings on other sequence or at request of DMC: T1-weighted MRI with Gd-contrast.

[REDACTED]

The duration of the MRIs will be approximately 50 minutes.

Centralized reading of the safety MRIs will be implemented through an Imaging vendor. The local site medical interpretation (by a radiologist or a neurologist or another qualified medical personnel) will be used by the investigator for immediate attention to clinically significant findings; however the assessment from the central reader will be captured in the database and used for reporting purposes. Therefore, MRIs are required to be scheduled in advance (i.e. at the latest 2 weeks prior) of the next drug administration/dispensing visit to verify safety findings before the bottles are dispensed.

MRI scans will be archived as source documents at the investigator's site. The de-identified MRI scans will be transferred by the site to the Imaging vendor (refer to the Imaging Manual provided by the Imaging vendor at study start).

Final interpretation, including assessment of Amyloid Related Imaging Abnormality (ARIA) ([Sperling et al 2011](#)) and white matter disease including hyperintensities ([Wahlund et al 2001](#)) will be provided to the site by the Imaging vendor as source documents at the investigator's site.

In case of new findings identified on MRI scans or if required by the DMC, gadolinium, a contrast agent, will be used at an unscheduled MRI T1 scan to investigate disruption of the blood-brain barrier as a sign of acute inflammation. In such case, gadolinium (e.g. Gadovist®-Diethylenetriamine Pentaacetic Acid (DPTA) [0.1 mmol/kg]) will be injected as a slow bolus as per local product information. Creatinine clearance estimate will be checked by the investigator before administration of gadolinium.

MRI findings will be reported additionally as AEs only if they induce clinical signs or symptoms that are considered clinically significant. Guidance to the investigators in case of newly occurring findings is provided in [Appendix 1 Section 13.2](#).

Of note: investigators may request an unscheduled MRI for safety purposes at any time during the study.

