5.6.2 Discontinuation of study treatment

Participants may voluntarily discontinue the investigational treatment for any reason at any time. In case of permanent discontinuation or temporary suspension from study treatment, participants are encouraged to continue attending study visits and remain in the study. IRT should be notified of treatment discontinuation so that no further drug resupply is planned for this participant.

Participants who progress to MCI/dementia due to AD should continue on the investigational treatment. The investigator should discontinue the investigational treatment for a given participant if, overall, he/she believes that continuation would be detrimental to the participant's well-being.

Investigational treatment may also be discontinued at the individual or study level, following regular safety evaluations or futility analysis review by the DMC.

The following circumstances will require stopping further investigational drug administration, in the respective participant, as assessed by the investigator:

- In the case of progression to late-moderate or severe dementia or loss of capacity to consent, the participant should be discontinued from the study.
- Withdrawal of Informed Consent (participant wish, see [Section 5.6.3](#))
- In the unlikely event of Pregnancy (see [Section 7.6](#))
- Use of prohibited treatment leading to discontinuation of treatment as per [Table 5-1](#) or meeting criteria for treatment discontinuation with restricted medications listed in [Table 5-2](#)
- Any other protocol deviation or situation that results in a significant risk to the participant's safety
- Meeting the criteria for discontinuing the investigational treatment due to:
 - Diagnosis of dementia not due to AD after confirmation of diagnosis by the Progression Adjudication Committee (PAC)
 - Clinically significant results of safety assessments deemed to be related to investigational drug that might put the participant at risk, including, but not limited to MRI, laboratory tests, vital signs or ECG ([Appendix 1](#)).

In addition, investigational treatment should be suspended for participants when:

- Study partner is not available for a period of more than 3 months. When available again or a replacement study partner is identified, study treatment can be resumed
- They are taking medications listed in [Table 5-1](#) for an acute condition

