13.2 Neurological symptoms or signs

New neurological findings are defined as clinical signs or symptoms that raise concern in respect to neurological conditions.

They include but are not limited to:

- significant new or worsening neurological symptoms or signs, as reported spontaneously by the participants/caregivers at any time, or detected during the scheduled physical/neurological examinations or on MRI scans. These might be events such as new or worsening peripheral neuropathies, visual disturbances, or seizures;
- worsening of cognition not consistent with the previous clinical course, as reported spontaneously by the participants/caregivers at any time or observed at the clinical assessments (e.g. APCC, CDR-SOB, RBANS, NPI-Q).

Investigators will be asked to review the finding in consultation with an appointed neurologist (when applicable) and initiate any additional tests as needed. Summary of the findings will be provided for the attention of the Safety Monitor who will assess the need to consult the DMC, regardless of the suspected relationship to investigational treatment.

Further tests will be scheduled to monitor the time-course of the findings until resolution if possible, and detailed information on the results will be communicated to the DMC.

Discontinuation of study medication will be considered in case of clinically significant findings considered to be suspected to be related to study medication, as judged by investigator and DMC.

These findings will be reported additionally as AEs only if they are symptomatic (i.e. reported spontaneously and not only observed at scheduled assessments), require symptomatic treatment, or impact study medication (suspension or discontinuation).

In case MRI findings indicating CNS inflammation, additional clinical investigations including physical and neurological examinations and laboratory evaluations will be performed. Final interpretation of the safety MRI scans, including assessment of ARIA, white matter, stroke or other findings will be provided to the site by the Imaging vendor.

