2.8.1 Adverse events (AEs)

Treatment-emergent AEs (TEAEs) are events that either started after the first dose of study drug or events present prior to the start of study drug but increased in severity since the first dose. Adverse events reported within 31 days (5 half-lives) from study drug discontinuation date (i.e., last dose date) will be considered as TEAE. AEs reported more than 31 days after study drug discontinuation will not be considered treatment emergent (non-TEAE).

TEAEs and non-TEAEs will be summarized separately on the SAF.

Tables

TEAEs, SAEs, deaths and non-TEAEs will be summarized as follows

- TEAEs regardless of relationship to study drug by SOC, PT and maximum severity
- non-TEAEs, regardless of relationship to study drug by SOC and PT
- TEAEs causing study drug discontinuation by SOC, PT and maximum severity
- TEAEs related to study drug by SOC, PT and maximum severity
- TE-SAEs regardless of relationship to study drug by SOC and PT and maximum severity

Note: For missing information on AE relationship to study drug, the most conservative approach will be considered: If information on relationship of the AE to study drug is missing, the AE will be considered as related to study drug for reporting TEAEs.

The above summaries are generally without exposure adjustment, except from TEAEs by SOC and PT: this summary will be presented with exposure adjustment. The exposure-adjusted incidence rate of adverse events is defined as the number of participants with the adverse event divided by total participant years at risk in the treatment group. The time at risk for each participant will differ for each adverse event. For participants with events, only the time until the first event contributes to the total participant years at risk. For participants who do not experience the event, the time at risk will be calculated using the duration of exposure as defined in [Section 2.4.1](#). The exposure-adjusted incident rate will be summarized per 100 participant years. For participants with multiple occurrences of the same event, the event will be counted only once per participant.

Adverse events will be reported according to the latest MedDRA dictionary version available at the time of database lock.

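### Protocol Sections 6.4.7, 13.2, 7.1 and 6.4 differ on when an MRI finding is an adverse event, so a drug stop for a silent finding can be missing from the table of TEAEs causing discontinuation

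*Protocol*

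**What the plan says.** Four places in the protocol govern whether an MRI finding goes on the AE page.

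- **Section 6.4.7 (safety brain MRI):** "MRI findings will be reported additionally as AEs only if they induce clinical signs or symptoms that are considered clinically significant". What happens to study drug is not a criterion. The next sentence begins "Guidance to the investigators in case of newly occurring findings is provided in" and names Appendix 1, Section 13.2.
- **Section 13.2 (neurological symptoms or signs):** its first bullet extends to events "or detected during the scheduled physical/neurological examinations or on MRI scans". Its AE rule starts "These findings will be reported additionally as AEs only if they are symptomatic" and goes on to add findings that "require symptomatic treatment, or impact study medication (suspension or discontinuation").
- **Section 7.1 (under the laboratory test results subheading):** a laboratory value or test result is an AE only if it meets at least one of three criteria: it causes signs or symptoms, it is judged clinically significant, or it needs therapy.
- **Section 6.4 (opening text):** for all the safety assessments that follow, MRI included, the AE page is for clinically significant abnormalities. Symptoms are not mentioned.

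Section 5.6.2 requires study drug to be stopped when findings of clinical significance arise in "safety assessments deemed to be related to investigational drug that might put the participant at risk, including, but not limited to MRI", among other tests. It sets no symptom requirement.

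On the output side, Protocol Section 9.5.2 plans summaries of AEs leading to discontinuation and of AEs leading to dose adjustment. SAP Section 2.8.1 lists "TEAEs causing study drug discontinuation by SOC, PT and maximum severity".

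**The concern.** Scheduled MRI is meant to show changes such as ARIA or a new infarct, including changes the participant has not noticed. Section 5.6.2 foresees that such a result can end treatment. Whether that stop then carries an AE record depends on which of the four rules the site applied.

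The table of TEAEs causing discontinuation is where a reader looks for tolerability-driven stops by term and severity. If some sites recorded silent MRI-driven stops as AEs and others did not, the table undercounts by an unknown amount. The same records feed the tables of drug-related TEAEs (SAP Section 2.8.1) and of adverse events of special interest (SAP Section 2.8.1.1), which also count only AEs.

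**Working it through.** No arithmetic applies; the check compares texts. Take one case: a participant without symptoms has a new finding on a scheduled safety MRI. It is judged clinically significant and related to study drug, and drug is permanently stopped under Section 5.6.2.

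| Protocol section | Criterion the case could meet | AE recorded? |
|---|---|---|
| 6.4.7 | Clinically significant signs or symptoms: none | No |
| 13.2 | Symptomatic: no. Symptomatic treatment: none assumed. Study medication affected: yes | Qualifies |
| 7.1 | Signs or symptoms: no. Clinically significant: yes | Qualifies |
| 6.4 | Clinically significant: yes | Qualifies |

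Two details bear on this. First, a stop under Section 5.6.2 presupposes clinical significance, so the case meets 7.1 and 6.4 by construction. Second, Section 13.2 counts a finding as symptomatic when it is reported spontaneously, not when it is merely seen at a scheduled assessment. A finding seen only on a scheduled scan can then enter through 13.2 only by its treatment or study-medication criteria, and 6.4.7 has neither.

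Next, follow the case through the planned outputs.

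- **TEAEs causing discontinuation (SAP 2.8.1).** Absent under 6.4.7. Present under the other rules if an AE is recorded within the treatment-emergent window, which runs to 31 days after the last dose.
- **Safety MRI tables (SAP 2.8.4.4).** Any new ARIA-E is tabulated. ARIA-H is tabulated above thresholds, for example more than 4 new microhemorrhages. White matter disease is tabulated when the score rises. A new infarct has no table of its own.
- **Safety MRI listings (SAP 2.8.4.4).** New or worsening findings are listed, other abnormalities included, so the finding is visible here whatever its type.
- **Reasons for stopping treatment (SAP 2.3.1).** The primary reason is summarised and listed.

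So the case remains in the report. What 6.4.7 removes is the AE record, with its MedDRA term, severity and causality, and its place in the discontinuation table. Neither the MRI outputs nor the reasons for stopping are specified to join the finding to the stop.

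Suspensions meet the same conflict but belong in a different output. The protocol plans a summary of AEs leading to dose adjustment; the AE tables listed in SAP Section 2.8.1 do not include one.

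**The case against.** The strongest reply has four parts.

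**The rules are not strictly incompatible.** A reader might infer that a site cannot obey both 6.4.7 and 13.2. Taken literally, *only if* states a necessary condition, so recording no AE for a silent finding breaches neither sentence. This is correct. The conflict arises when each sentence is used as the complete recording rule, which is the natural use at a site because no other rule for MRI findings is given beside it.

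**Section 13.2 may not cover silent findings.** Its title and opening definition speak of clinical signs or symptoms. Against that, its first bullet names MRI scans, it has a separate study-medication criterion, and 6.4.7 sends investigators there for new MRI findings. A narrow reading is possible but not the better one. Section 7.1 has a similar limit, since its criteria stand under a laboratory heading, although they also name test results. Section 6.4 has no such limit.

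**Sites are pointed to the wider list.** The cross-reference in 6.4.7 does reduce the risk that 13.2 is overlooked. It does not say which rule prevails.

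**The findings are reported elsewhere.** A reader might infer that the cases which monitoring is meant to detect disappear. The documents do not support that. Central MRI reads are held in the database, the data monitoring committee receives them (Protocol Section 8.4), and the MRI outputs and reasons for stopping are in the SAP. The gap is confined to AE-based tables.

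**Conclusion.** The point holds as an inconsistency in AE recording with a specific consequence. By 6.4.7, a discontinuation for a symptomless MRI finding is missing from the table of TEAEs causing study drug discontinuation; by 13.2, 7.1 or 6.4 it can be present. No efficacy result is affected, and the MRI data themselves are still reported.

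The number affected cannot be stated, because the documents give no rate of drug stops for silent MRI findings. A reader might put an assumed 0.5% to 2% on the planned 2000 participants (0.005 × 2000 = 10; 0.02 × 2000 = 40). The documents support neither factor: the rates have no source in them, and SAP Section 1.1.1 says the planned enrolment will not be reached.

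The conclusion rests on two assumptions: that sites used the quoted sentences as working rules for the AE page, and that at least one such stop occurred. The second can be checked in the data.

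**What to change.** **Protocol text.** Reconcile Sections 6.4, 6.4.7, 7.1 and 13.2 into one AE-recording rule for MRI findings. Section 6.4.7 should carry the three criteria of 13.2 as 13.2 words them (symptomatic, requiring symptomatic treatment, or having an impact on study medication), and the result should agree with 7.1 on clinical significance. This concerns recording only; it changes no rule on when drug is stopped. Treatment ended in July 2019, so the edit cannot alter how these data were collected.

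**Data already collected.** The SAP change log has entries after database lock, so the practical step is a cross-check. Match treatment discontinuations, with their recorded reasons, against the safety MRI listings and the AE records. Where a discontinuation is attributed to an MRI finding and has no matching AE, add a footnote to the table of TEAEs causing discontinuation with the count by arm. Do not assign terms or severity after lock to place such cases in the body of the table. Report suspensions separately.

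**Cost.** A few sentences of protocol text, one programmed match of existing datasets, and a footnote. No further assessments are needed, and the locked database is not reopened.
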